### **8.1.3 Screening, visit 2**

All screening assessments as described in section [2](#) must be performed. V2 must be at least 1 day after V1, and V2 must be at least 5 days before V3.

### **8.1.4 Screening failures**

For screening failures the screening failure form in the case report form (CRF) must be completed with the reason for not continuing in the trial. Serious and non-serious adverse events from screening failures must be transcribed by the investigator into the CRF. Follow-up of serious adverse events (SAEs) must be carried out according to section [12](#).

A screening failure session must be made in the IV/WRS. The case book must be signed.

### **8.1.5 Re-screening**

Re-screening of screening failures is allowed however there must be at least 90 days from screen failure date to re-screening. In case of re-screening, a new informed consent and assent must be obtained, a new screening number must be allocated and samples and assessments must be performed once more according to the screening procedures. For more information see section [10](#).

### **8.1.6 Randomisation, visit 3**

Subject eligibility must be evaluated according to the inclusion and exclusion criteria. To randomise a subject a randomisation session must be performed in IV/WRS. The Tanner stage, HbA1c and FPG result from V2 must be entered in IV/WRS (section [11](#)).

The subject must be instructed in handling of the pen and the trial product (section [9](#)) including training in injection site (section [5.3](#)) and injection technique. The subject should be instructed to perform an air shot before the use of a new pre-filled pen. At all subsequent visits, subjects should be trained at the investigators discretion.

Protocol: Liraglutide  
Trial ID: NN8022-4179  
UTN: U1111-1162-7884  
EudraCT no.: 2014-004415-37

CONFIDENTIAL

Date: 16 July 2020  
Version: 5.0  
Status: Final  
Page: 44 of 125

Novo Nordisk

The first dose of trial product must be injected by the subject or their LAR at the site.

For training in recognition of hypoglycaemia, see section [8.5.2](#) and for instruction in handling of the blood glucose (BG) meter including auxiliaries and self-measured blood glucose (SMBG), see sections [8.5.2.1](#).

### **8.1.7 Dose escalation, visit 4-7**

At each visit during the dose escalation period, a measurement of the subject's plasma glucose level by self-monitored blood glucose (section [8.5.2.1](#)) must be performed before instructing the subject in dose escalation. For dose escalation see section [5.3.1](#).

### **8.1.8 Discontinuation of trial product**

See section [6.4](#) for discontinuation of trial product criteria. For subjects with discontinuation of trial product, the investigator must at a minimum aim to:

- undertake procedures for the end of treatment visit (V19) as soon as possible and
- schedule a follow up visit (V20) two weeks later.

Depending on when the discontinuation of trial product takes place during the trial:

- If trial product is discontinued between V3 and V9, the subject should attend V10x (16 weeks after V3) and V19x (52 weeks ( $\pm$  5 days) after V3)
- If trial product is discontinued between V11 and V19, the subject should attend V19x (52 weeks ( $\pm$  5 days) after V3)

The end-of-trial form must be completed, and final drug accountability must be performed. A treatment discontinuation session must be made in the IV/WRS. The case book must be signed.

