Dispense menstrual period diary 8.7.3.3			x																			

Protocol: Liraglutide  
 Trial ID: NN8022-4179

UTN: U1111-1162-7884  
 EudraCT no.: 2014-004415-37

Date:  
 Version:

16 July 2020 | Status:  
 5.0 | Page:

Final  
 20 of 125 | **Novo Nordisk**

Trial Periods	Screening	Screening	Randomisation	Dose escalation			Double blind treatment			Open-label treatment						End of treatment	Follow-up	TPD 16 week FU	TPD 52 week FU			
				4	5	6	7	8	9	10 	11	12 	13	14 	15 					16	17 	18 
Visit number	1 	2 	3	4	5	6	7	8	9	10 	11	12 	13	14 	15 	16	17 	18 	19	20	10x	19x
Timing of visit (weeks)	-2		0	1	2	3	4	8	12	16	20	24	28	32	36	40	44	48	52	54	16	52
Visit window (days)				±2	±2	±2	±2	±5	±5	±5	±5	±5	±5	±5	±5	±5	±5	±5	±5	-5	±5	±5
Collect menstrual period diary				x	x	x	x	x	x	x	x	x	x	x	x	x	x	x	x	x		
Attend visit fasting 8.1.3		x	x							x						x			x	x 		

Abbreviation list: TPD = trial product discontinuation, FU = follow up, SMBG = self-measured blood glucose, PHQ-9 = Patient Health Questionnaire 9, C-SSRS = Columbia Suicidality Severity Rating Scale, V = visit, BG = blood glucose, IV/WRS = interactive voice/web response system, ECG = electrocardiogram, hsCRP = high sensitivity C reactive protein.

Protocol 4179-protocol-version-5.0.1  
 NN8022 -4179

Protocol: Liraglutide  
 Trial ID: NN8022-4179

UTN: U1111-1162-7884  
 EudraCT no.: 2014-004415-37

Date:  
 Version:

16 July 2020  
 5.0

Status: Final  
 Page: 21 of 125  
 Novo Nordisk

Footer	Description
1	Maximum two weeks between V1 and V3. V2 must be at least 1 day after V1, and V2 must be at least 5 days before V3, to ensure blood samples are available for randomisation.
2	All assessments at V10 should be performed prior to trial medication dispensing, as the trial medication dispensing session in IV/WRS as V10 will un-blind subject's treatment.
3	Home visits possible for subjects treated with liraglutide placebo only.
4	At V2 all pre-existing conditions should be reported as medical history or concomitant illness.
5	Visit can be performed as phone/video conference visit.
6	Only for females of childbearing potential. At V2 and V19 performed as serum pregnancy test and from V3-V18 urine-stick pregnancy test, if applicable 8.5.5 .

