Subjects will be randomised 2:1 to receive liraglutide or liraglutide placebo. Part A has four strata as subjects are stratified according to Tanner stage 2–3 and 4–5 and by presence/absence of dysglycaemia. Part B includes subjects with Tanner below 2 (defined as Tanner stage 1 with or without premature adrenarche) and has two strata for presence/absence of dysglycaemia, see section [11](#).

Dysglycaemia is defined as pre-diabetes with FPG 5.6 – 6.9 mmol/L (both inclusive) (100-125 mg/dL) (both inclusive) and/or HbA1c 5.7 – 6.4 % (both inclusive). The HbA1c and FPG results from V2 must be used.

At least 30% of subjects will be from areas with lifestyle and nutrition comparable to that in the European Union (EU). All subjects and/or their legally acceptable representative (LAR) will undergo counselling for weight loss and must be prescribed a structured programme for diet and physical activity throughout the trial (from randomisation to the end of the trial). Placebo injections will be stopped at week 16, at the end of the double-blind period.

Subjects treated with growth hormone therapy may enter the trial and will have no change in treatment plan with growth hormone from randomisation to the end of the open-label period (subjects on growth hormone will stay on, and subjects off growth hormone will stay off during this period. Adjustments to doses of growth hormone are permitted).

Protocol: Liraglutide  
Trial ID: NN8022-4179  
UTN: U1111-1162-7884  
EudraCT no.: 2014-004415-37

~~CONFIDENTIAL~~

Date: 16 July 2020  
Version: 5.0  
Status: Final  
Page: 30 of 125

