**Table 4-1 Overview of subject analysis set**

Subject Analysis Set	Description
Full Analysis Set	All randomised subjects who have received at least one dose of trial product and have any post-randomisation data. The statistical evaluation of the FAS will follow the intention-to-treat (ITT) principle and subjects will contribute to the evaluation “as randomised”.
Safety Analysis Set	All subjects exposed to at least one dose of trial product. Subjects in the SAS will contribute to the evaluation “as treated”.

Data from nominal visits (V10x and V19x) will be used prior to imputation of remaining missing data unless otherwise stated.

Before data are locked for statistical analysis, a blind review of all data will take place. Any decision to exclude a subject or single observation from the statistical analysis is the joint responsibility of the trial statistician, the ITM and the medical specialist. Exclusion of data from analyses will be used restrictively and normally no data should be excluded from the FAS. The subjects or observations to be excluded, and the reasons for their exclusion must be documented and signed by those responsible before database lock. The subjects and observations excluded from analysis sets, and the reason for this, will be described in the clinical trial report.

Any observation excluded from the analysis database will be documented before database lock with the reason for exclusion provided.

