### 6.3.2.2 Visits windows

Generally, visit-windows will be used for the data that is summarized by visit; they are based on the study evaluation schedule and comprise a set of days around the nominal visit day. For any assessment, there are the protocol defined scheduled visits around which visit windows were created to cover the complete range of days within the study.

In 4179 the visit windowing will be done only for V10 and V19 visits for prematurely discontinued/withdrawn subjects.

The visit windows are shown in [Table 6-2](#).

In this table, the days are counted since the date of randomization for both safety and efficacy assessments. These visit windows apply to measurements taken at every visit. For assessments collected less often different visit windows will be applied as detailed below.

When visit windows are used, all visits will be re-aligned, i.e., they will be mapped into one of the visit windows. For example, if the Week 4 visit of a subject is delayed and occurs on Day 46 instead of on Day 29, it will be re-aligned to visit window Week 8. In the case of major deviations from the visit schedule, or due to unscheduled visits, several assessments of a subject may fall in a particular visit window (either scheduled or unscheduled). Statistical approaches to handle multiple assessments in a given visit window are specified below.

In general, if two consecutive visits  $V_t$  and  $V_s$  are  $x$  days apart, the upper limit of the visit window for  $V_t$  will be  $V_t+x/2$  and the lower limit for the visit  $V_s$  will be  $V_s-x/2$  (if  $x$  is even, the lower limit for  $V_s$  will be  $V_s-x/2+1$ , and the upper limit for  $V_t$  will be  $V_t+x/2$ ). The algorithm needs to ensure that visit windows are not overlapping and that there are no gaps, such that each assessment can be uniquely allocated to one visit window, e.g., if Week 8 visit is scheduled for day 57, Week 12 is scheduled at Day 85 and Week 16 is scheduled at Day 113, then the visit window for week 12 extends from Day 79 to Day 106.

Note: The lower limit of first visit will be assigned with -999 which accommodate all assessments occurred before the scheduled day.

The upper limit of last visit will be assigned with 999 which accommodate all assessments occurred after the scheduled day.

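### Premature stops of trial product in weeks 12 to 20 are assigned no retrieval visit, so the week-52 value, and for some the week-16 value, is left to placebo-based imputation

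*Protocol*

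**What the plan says.** Protocol 8.1.8 sets two conditions for retrieval after trial product is stopped. The early one reads "If trial product is discontinued between V3 and V9, the subject should attend V10x (16 weeks after V3) and V19x". The late one reads "If trial product is discontinued between V11 and V19, the subject should attend V19x". SAP 6.3.2.1 repeats both intervals. In the flow chart V9, V10 and V11 are at weeks 12, 16 and 20. Its columns for 10x and 19x are headed as follow-up after trial product discontinuation and carry no rule on who attends.

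For every subject who stops, section 8.1.8 also asks the investigator to "undertake procedures for the end of treatment visit (V19) as soon as possible and" to schedule V20 two weeks later.

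The retrieved values matter to the main analysis. SAP section 4, like protocol 17.2, says: "Data from nominal visits (V10x and V19x) will be used prior to imputation of remaining missing data unless otherwise stated". SAP 5.3.2.2 then imputes whatever is still missing, in both arms, from the placebo group.

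Three further statements decide who loses what:
- Week-16 data for subjects still on product come from V10 itself: "All assessments at V10 should be performed prior to trial medication dispensing" (flow chart, footnote 2).
- Placebo product ends by design: "Placebo injections will be stopped at week 16, at the end of the double-blind period" (protocol 5.1).
- Early records are re-dated by study day: "In 4179 the visit windowing will be done only for V10 and V19 visits for prematurely discontinued/withdrawn subjects" (SAP 6.3.2.2).

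**The concern.** The two intervals do not meet. A subject who stops after V9 and before V11 meets neither condition, so the text asks for no V10x and no V19x. This includes a premature stop at V10 itself, when allocation has just been revealed.

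The protocol calls the primary estimate an intention-to-treat or effectiveness estimate, and the SAP defines a class of retrieved drop-outs for it (Table 5-2). For subjects in the gap, a landmark value that could have been measured becomes one that is modelled. In the liraglutide arm it is replaced by a draw from the placebo model. In the placebo arm, a stop between V9 and V10 also removes an observation from the data that fit that model. The model is demanding for at most 19 placebo subjects. By SAP Table 5-3 it has 1 intercept + 1 sex + 3 region + 2 Tanner + 1 glycaemic + 2 interaction + 1 baseline BMI SDS = 11 coefficients. The plan already foresees that it may not be estimable.

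**Working it through.** **Who loses which value.** From SAP Table 6-2, V9 is day 85, V10 day 113 and V11 day 141. The week-16 window is days 107-134 and the week-52 window is days 359-371. From Table 6-3, a height measured before day 107 is assigned to V3.

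- *Stop between V9 and V10 (days 86-112, 27 days).* No V10x or V19x is assigned. If the early V19 falls on day 107 or later, weight and height are re-dated to week 16 and the value is kept. If it falls earlier, weight goes to the week-12 window and height to V3, so there is no week-16 BMI SDS. If the early V19 takes place on the day of stopping, the loss covers days 86-106, which is 21 of the 27 days. V20 does not rescue the value: the flow chart marks weight but not height there, and SAP re-dating is limited to V10 and V19. Week 52 is lost in every case.
- *Stop between V10 and V11 (liraglutide only, because placebo product ends at week 16).* Week 16 was already measured at V10. The early V19 falls more than 200 days before day 359, so week 52 is lost.

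**How many.** The documents give no rate or timing for product discontinuation. As a proxy, take the planned withdrawal of 10% by week 16 and 20% by week 52 (protocol 17.1).

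- Weeks 12-16: 57 × 0.10 × f, where f is the assumed share of week-16 drop-outs falling in those four weeks.
  - f = 0.10 gives 0.57.
  - f = 0.25 (even spread, 4/16) gives 1.43, of which 38 × 0.10 × 0.25 = 0.95 are on liraglutide.
  - f = 0.50 gives 2.85.
- Weeks 16-20, liraglutide only, even spread of the further 10%: 38 × 0.10 × 4/36 = 0.42.

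**The plan's own sample size.** Protocol 17.1 uses a difference of 0.23, SD 0.25, withdrawal p = 0.10, 2:1 allocation, 5% two-sided and 80% power.

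- Corrected difference: (1 − 0.10) × 0.23 = 0.207.
- Corrected variance: 0.25² + (2/3)(0.10)(0.90)(0.23²) = 0.0625 + 0.0032 = 0.0657, so SD = 0.2563.
- The normal approximation gives 19 placebo and 38 liraglutide subjects, 57 in total, as stated. (Several other cells of Table 17-1 come out 3 lower this way, which does not bear on this point.)
- Power at 19 and 38: 0.207 / (0.2563 × √(1/19 + 1/38)) = 2.87; 2.87 − 1.96 = 0.91; power 0.820.

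**Effect of closing the gap at week 16.** With f = 0.25 and every such subject retrieved, p falls from 0.10 to 0.075. The corrected difference becomes 0.2128, the SD 0.2548 and the power 0.844. This is an upper bound at that share, because it assumes that retrieved subjects keep the full effect.

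**Dilution per subject.** One liraglutide subject imputed as placebo shrinks the assumed week-16 difference by at most 0.23 × 1/38 = 0.006 SDS, or 2.6%. No week-52 effect size is stated, so for that endpoint only the relative figure of 1/38 applies.

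**The case against.** Sites have more than one sentence to work from. The flow-chart columns for the retrieval visits are not limited by date of stopping, and protocol 8.1 makes the investigator responsible for visits occurring as the flow chart shows. The early interval might also be meant by last visit attended, which would cover stops between V9 and V10. These readings are possible but not stated, and the last-visit reading still leaves V10 to V11 open. A site following section 8.1.8 literally would not schedule the visit.

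Three stronger inferences are tempting, and the documents do not support them.

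- *Everyone stopping between V9 and V11 loses week-16 data.* Those on product at V10 are measured there before dispensing, and some earlier stops are recovered through the day-107 window.
- *About two of 57 subjects are affected.* That figure applies withdrawal rates to product discontinuation and assumes even timing. Protocol 8.1.9 treats consent withdrawal separately and asks those subjects for neither retrieval visit, so closing the gap would not retrieve them. Protocol 18.1 places onset of the most frequent adverse events in weeks 1-4, which suggests earlier stops.
- *The sample size or power is undermined.* The calculation already treats every withdrawn subject as a placebo responder.

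The objection also stands on the remedy. A rule that simply routes every stop from V10 onward to V19x would catch all placebo subjects, whose injections end at week 16 by design. V19x has a reduced set of assessments, and SAP 5.3.3 excludes it from all four sensitivity analyses.

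**Conclusion.** The gap is in the text of both documents and bears on both co-primary endpoints, but mainly on week 52. Followed as written, every premature stop between V9 and V11 loses the week-52 value. Only stops between V9 and V10 with an early V19 before day 107 also lose week 16.

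The number of subjects cannot be derived from the documents. On the proxy and range above it is about 0.6 to 2.9 of 57, plus about 0.4 on liraglutide in weeks 16-20. Each liraglutide subject imputed as placebo moves the difference by at most 1/38 of the effect, towards zero. That direction rests on the plan's own premise that subjects who stop liraglutide do no worse than placebo. The 57 subjects and the stated power stand. The point is worth correcting because the loss is avoidable and the visits already exist, not because the trial's conclusion hangs on it.

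**What to change.** In protocol 8.1.8, use adjoining intervals for premature discontinuation:

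- Stopped after V3 and before the V10 assessments: attend V10x and V19x.
- Stopped prematurely at or after V10 and before V19: attend V19x.
- The planned end of placebo injections at week 16 is not a premature discontinuation; those subjects continue with the regular V11 to V19 visits.

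SAP 6.3.2.1 describes in the past tense what subjects were asked to do, so rewriting the rule there would collect no data and would misstate the instruction given. Instead, the SAP should:

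- report how many subjects in each arm stopped product between V9 and V11, and how many of them lack a week-16 or week-52 value;
- use any weight and height obtained within the landmark windows, whatever the visit label.

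The cost is a few sentences in each document. The protocol change needs an amendment with the approvals set out in protocol section 25, and it helps only subjects who have not yet passed these visits. No new visit type is needed and the sample size does not change.

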### **8.1.9 Withdrawal of informed consent/assent**

See section [6.5](#) for withdrawal criteria. If a subject and/or their LAR withdraw informed consent/assent the investigator must aim to undertake procedures similar to those for the end of treatment (V19) as soon as possible and the follow up visit (V20) two weeks later.

The end-of-trial form must be completed, and final drug accountability must be performed even if the subject is not able to come to the trial site. A treatment discontinuation session must be made in the IV/WRS. The case book must be signed.

Although a subject is not obliged to give his/her reason(s) for withdrawing from a trial, the investigator must make a reasonable effort to ascertain the reason(s), while fully respecting the subject's rights. Where the reasons are obtained, the primary reason for not completing the trial must be specified on the end-of-trial form in the CRF.

Protocol: Liraglutide  
Trial ID: NN8022-4179  
UTN: U1111-1162-7884  
EudraCT no.: 2014-004415-37

~~CONFIDENTIAL~~

Date: 16 July 2020  
Version: 5.0  
Status: Final  
Page: 45 of 125

**Novo Nordisk**

### 8.1.10 Home visits

Selected site visits as indicated in the flow chart (section [2](#)) can be converted to home visits during the open-label period for subjects in the liraglutide placebo group. The selected visits have no scheduled drug dispensing, blood sampling, ECG measurement, or physical examination.

Site staff must bring the following equipment during the home visit:

- Calibrated transportable scale
- Calibrated blood pressure monitor
- Measuring tape for measurement of waist and hips
- Urine sticks (applicable when females of childbearing potential are visited only)
- Equipment for pulse measurement
- BG meter for finger prick test (in case subject's own BG meter is not available)
- PHQ-9 questionnaire (self-completed by subjects)
- C-SSRS questionnaire:
  - questionnaire to be completed at home (if home visit is conducted by site staff certified as C-SSRS interviewer) or
  - set-up of telephone/video conference interview (if home visit is not conducted by site staff certified as C-SSRS interviewer)

Documentation for remaining assessments as per the flowchart (concomitant medication, adverse event, review and collection of menstrual information diary information etc.) must be obtained during the home visit. The site dietitian must be informed that the site visit is converted to a home visit so a telephone/video conference contact to the subject can be established.

## 8.2 Laboratory assessments

Laboratory assessments are performed by a central laboratory except for assessments for liraglutide plasma concentration and anti-liraglutide antibodies that are analysed by special laboratories.

Descriptions of laboratory supplies and procedures for obtaining samples, handling and storage of samples including reporting of results and information regarding who will perform the assessments are described in a trial-specific laboratory manual provided by the central laboratory.

For a list of blood samples for efficacy assessment, see section [8.4.4](#) and for a list of blood samples for safety assessments, see section [8.5.7](#). For description of samples for liraglutide plasma concentration samples, see section [8.7.1](#) and for anti-liraglutide antibodies, see section [8.5.8](#).

No additional central laboratory assessments than those described in the protocol (section [2](#)) are allowed.

Protocol: Liraglutide  
 Trial ID: NN8022-4179  
 UTN: U1111-1162-7884  
 EudraCT no.: 2014-004415-37

**CONFIDENTIAL**

Date: 16 July 2020  
 Version: 5.0  
 Status: Final  
 Page: 46 of 125  
**Novo Nordisk**

All laboratory samples except for the liraglutide plasma concentration samples and the anti-liraglutide antibody samples are sent to the central laboratory, analysed and reported to the investigator on an ongoing basis.

Blood samples for liraglutide plasma concentration and anti-liraglutide antibodies are sent for storage only at the central laboratory and later sent to the special laboratory for analysis at specific time intervals. Furthermore, selected blood samples for anti-liraglutide antibodies are sent from the special laboratory to Novo Nordisk A/S for further characterisation, see section [8.5.8](#)

The antibody samples are analysed before LPLV but results will not be reported to the investigator as these results will not be used for any clinical evaluation during the course of the trial. The results of the antibody samples will only be reported to the investigator upon request at the end of trial.

Laboratory samples are destroyed on an ongoing basis or at the latest at the completion of the clinical trial report, except for antibody samples.

Antibody samples may be retained until approval of the paediatric indication by FDA and/or EMA or up to a period of 15 years. The retained antibody samples may be used for further characterisation of antibody responses towards drug if required by health authorities or for safety reasons, see section [24.2](#).

